8. PATIENT ACCOUNTING AND DISPOSITION

8.1. Patient Disposition

Information for this presentation of the recorded data will come from the **Study Exit** case report form and the **Procedure** form. A complete accounting of patient participation in the study by analysis population will be presented in Table 14.1.1a entitled *Patient Accounting* using the Level 1 table design. The purpose of this table is to provide an accounting of patients from their entrance into the study through the final visit and to account for the evaluations of patients in the analyses of efficacy and safety, including reasons for early study termination. The overall number of patients reported in this table will be based on the number of patients consented and the reasons for screen failure.

Each listing will contain separate flags to indicate if the patient is part of the ITT, FAS and Per-Protocol populations, respectively. Listing 16.1 entitled *Patient Disposition* supports Tables 14.1.1a through 14.1.1.2. This listing will be sorted by site number and patient number. Listing 16.2.1 entitled *Inclusion Criteria* displays the data from the Inclusion Criteria case report form. The data will be displayed for each patient and for each inclusion criterion. Listing 16.2.2 entitled *Exclusion Criteria* displays the data from the Exclusion Criteria case report form. The data will be displayed for each patient and for each exclusion criterion. Listing 16.3.1 entitled *Protocol Deviations* will list all protocol deviations for each patient, and identify if they are major. The deviation code and description, visit and action, will also be included in the listing. The list of what constitutes a major deviation will be finalized prior to database lock.

8.2. Patient Demographics Recorded at Baseline

Case Report Form Data Source: Demographics [Date of Birth, Sex, Child-bearing potential, Ethnicity, Race, age, Date of ICF] / Visit: Screening and Baseline

Data will be summarized and reported in Table 14.1.2 entitled *Summary of Patient Demographics* (ITT population) using the Level 1 table design; Table 14.1.2a will be restricted to the ITT population. This table summarizes the patient population with respect to age at entry into the study, sex, weight, height, and BMI. Age will be reported in years. Age, weight (lbs.), height (inches) and BMI will be summarized using descriptive statistics: n, arithmetic mean, standard deviation, median, and range (*i.e.*, minimum and maximum values). Age will also be presented in mutually-exclusive categories: ≥ 65 to < 65 , years of age. Sex will be summarized using counts and percentages. Patients with missing data that cannot be resolved prior to database lock will not be included in the tabulation and excluded from the summary statistics; all demographic data will be presented in a listing. Sites that do not provide the full date of birth for a patient will not be considered missing data if the day of birth is not provided. Under this scenario, the first day of the month will be used in the calculations.

The supportive data for Tables 14.1.2 and 14.1.2a will be presented in Listing 16.4.1 entitled *Patient Demographics*. This listing will be sorted by site number and patient number and contain a separate flag to indicate if the patient is part of the FAS and Per-Protocol populations, respectively.

8.3. Medical History Recorded at Baseline

Information for this presentation of the recorded data will come from the **Medical History** case report form. Data will be summarized and reported in Table 14.1.3 entitled *Summary of Patient Medical History* (ITT population) using the Level 1 table design; Table 14.1.3a will be restricted to the FAS population. This table summarizes the patient population with respect to risk factors using counts and percentages. Patients with missing data that cannot be resolved prior to database lock will not be included in the tabulation and excluded from the summary statistics; all risk factor data will be presented in a listing.

The supportive data for Tables 14.1.3 and 14.1.3a will be presented in Listing 16.4.2 entitled *Medical History*. This listing will be sorted by Diabetes Site number, Endoscopy Site number and patient number and contain a separate flag to indicate if the patient is part of the FAS and PP populations, respectively.

8.4. Index Procedure and Hospital Admission Details

Information for this presentation of the recorded data will come from the **Index Procedure** case report form. Data will be summarized and reported in Table 14.1.4 entitled *Summary of the Index Procedure and Hospital Admission Details* (ITT population) using the Level 1 table design; Table 14.1.4a will be restricted to the FAS population.

The supportive data for Tables 14.1.4 and 14.1.4a will be presented in Listing 16.4.3 entitled *Index Procedure and Hospital Admission Details*. This listing will be sorted by site number and patient number and contain a separate flag to indicate if the patient is part of the FAS and PP populations, respectively.

8.5. Laboratory Tests

Information for this presentation of the recorded data will come from the **Laboratory Tests** case report form. Data will be summarized and reported in Table 14.1.5 entitled *Summary of the Laboratory Tests Recorded Prior to the Procedure* (ITT population) using the Level 1 table design; Table 14.1.5a will be restricted to the FAS population. The following laboratory values will be summarized based on the construct of the variable using the ITT population: continuous, multinomial, or binary.

Each laboratory parameter recorded on a continuous scale will be summarized using descriptive statistics: n, mean, standard deviation, median, minimum and maximum values. Patients with missing data that cannot be resolved prior to database lock will not be included in the tabulation and excluded from the summary statistics.

The supportive data for Tables 14.1.5 and 14.1.5a will be presented in Listing 16.4.4 entitled *Laboratory Tests*. This listing will be sorted by site number and patient number and contain a separate flag to indicate if the patient is part of the FAS and Per-Protocol populations, respectively. Unscheduled laboratory tests entered into the EDC system will also be contained within the listing.

8.6. Unscheduled Visit Information

Information for this presentation of the recorded data will come from the individual datasets where the visit name is listed as *Unscheduled*. Listing 16.4.9 entitled *Unscheduled Visit Information* will be sorted by site number, and patient.

The table below provides the specification for assignment of an unscheduled visit. If there are multiple records within an interval, date of the latest record will be used.

Visit Name	Clinic (Visit) / (R)emote Visit	Timing of the Visit (weeks)	Protocol Visit Window			Expanded Visit Window		
			Protocol Visit Window (days)	First Interval Day	Last Interval Day	First Interval Day	Last Interval Day	Expanded Visit Window (days)
Screening	R1	-12	-84 to -5	-84	-5			
Baseline[1]	V2	-3	-28 to -1	-28	-1			
Index Procedure	V3	0						
Week 1	R4	1	±2	5	9	5	9	2
Week 2	R5	2	±3	11	17	10	18	4
Week 4	V6	4	±5	23	33	19	37	9
Week 8	R7	8	±7	49	63	38	74	18
Week 12	R8	12	±7	77	91	73	95	11
Week 16	R9	16	±7	105	119	96	128	16
Week 20	R10	20	±7	133	147	129	151	11
Week 24	V11	24	±7	161	175	152	184	16
Week 28	R12	28	±7	189	203	185	207	11
Week 32	R13	32	±7	217	231	208	240	16
Week 36	V14	36	±7	245	259	241	263	11
Week 40	R15	40	±17	273	287	264	296	16
Week 44	R16	44	±7	301	315	295	321	13
Week 48 (End of Study)	V17	48	30	306	366	322	366	14

Visit Name	Clinic (Visit) / (R)emote Visit	Timing of the Visit (weeks)	Target Visit Day	Number of Days on Either Side of the Target Day to define the Expanded Time Window
Screening	R1	-12		
Baseline[1]	V2	-3		
Index Procedure	V3	0		
Week 1	R4	1	7	2
Week 2	R5	2	14	4
Week 4	V6	4	28	9
Week 8	R7	8	56	18
Week 12	R8	12	84	11
Week 16	R9	16	112	16
Week 20	R10	20	140	11
Week 24	V11	24	168	16
Week 28	R12	28	196	11
Week 32	R13	32	224	16
Week 36	V14	36	252	11
Week 40	R15	40	280	16
Week 44	R16	44	308	13
Week 48 (End of Study)	V17	48	336	14

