APPENDIX 2. SCHEDULE OF ACTIVITIES

	Screening															Week 48					
		Baseline ^[1]		Index Procedure	Week 1	Week 2	Week 4	Week 8	Week 12	Week 16	Week 20	Week 24	Week 28	Week 32	Week 36	Week 40	Week 44	Week 48	End of Study	Premature discontinuation within 24 weeks	Pre-mature discontinuation post 24 weeks
Clinic Visit(V)/Remote Visit (R)	R1	V2	V3	R4	R5	V6	R7	R8	R9	R10	V11	R12	R13	V14	R15	R16	V17	V17A	R17A		
Timing of visit (weeks)	-12	-3	0	1	2	4	8	12	16	20	24	28	32	36	40	44	48				
Visit window (days)	-84 to -5	-28 to -1		±2	±3	±5	±7	±7	±7	±7	±7	±7	±7	±7	±7	±7	±7	+30			
SUBJECT RELATED INFO/ASSESSMENTS																					
Informed consent	X																				
In/exclusion criteria	X	X																			
Medical history	X																				
Concomitant medication	X	X	X	X		X		X			X			X				X	X	X	
Demographics	X																				
Diabetes history	X																				
Diabetes medication review	X	X	X	X	X	X	X	X	X	X	X	X	X	X	X	X	X	X	X		
Lifestyle Counseling			X	X	X	X	X	X	X	X	X	X	X	X	X	X	X	X	X		
Diabetes education, Handout and instruct in CGM use			X																		
Handout ID card				X																	
Study Exit																		X	X	X	
VITAL SIGNS AND PHYSICAL EXAMINATION																					
Height			X																		
Body weight		X		X		X		X		X		X		X		X		X	X		
BMI		X		X		X		X		X		X		X		X		X	X		
Waist circumference		X						X		X		X		X		X		X	X		
Blood pressure and pulse rate		X	X			X		X		X		X		X		X		X	X		
Physical examination		X																X	X		
LABORATORY TESTINGS																					
Fasting plasma glucose			X			X		X ^[6]			X			X		X		X ^[6]	X		
HbA1c	X	X				X		X		X		X		X		X		X	X		
Fasting insulin		X				X		X ^[6]			X			X		X		X ^[6]	X		

	Screening	Baseline ^[1]	Index Procedure	Week 1	Week 2	Week 4	Week 8	Week 12	Week 16	Week 20	Week 24	Week 28	Week 32	Week 36	Week 40	Week 44	Week 48 End of Study	Premature discontinuation within 24 weeks	Pre-mature discontinuation post 24 weeks
Clinic Visit(V)/Remote Visit (R)	R1	V2	V3	R4	R5	V6	R7	R8	R9	R10	V11	R12	R13	V14	R15	R16	V17	V17A	R17A
Timing of visit (weeks)	-12	-3	0	1	2	4	8	12	16	20	24	28	32	36	40	44	48		
Visit window (days)	-84 to -5	-28 to -1		±2	±3	±5	±7	±7	±7	±7	±7	±7	±7	±7	±7	±7	+30		
Fasting serum C-peptide	X										X								
MMTT (Mixed meal tolerance test)			X					X									X	X	
HOMA-IR			X			X		X			X			X			X	X	
Fasting lipid panel			X								X						X	X	
Metabolic Panel ^[2]	X	X		X				X			X			X			X	X	
Pancreatic Enzyme (Lipase, Amylase)		X		X															

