The *Level 3* display will be used for summarizing the parameters recorded multiple times during the follow-up visits. An example of the layout is presented below; rows will be repeated for all visits where a measurement is recorded using the expanded time windows.

Level 3a Display

Parameter and Statistic	Observation Time	Device Generation 1 / 600 Volts / Single Treatment	Device Generation 1 / 600 Volts / Double Treatment	Device Generation 2 / 750 Volts / Double Treatment	All Patients
HbA1c	Baseline				
HbA1c	Post-Procedure Visit xxx				
HbA1c	Change from Baseline				

Level 3b Display

Parameter and Statistic	Observation Time	Device Generation 1 / 600 Volts / Single Treatment	Device Generation 1 / 600 Volts / Double Treatment and Device Generation 2 / 750 Volts / Double Treatment	All Patients
HbA1c	Baseline			
HbA1c	Post-Procedure Visit xxx			
HbA1c	Change from Baseline			

There will be 2 sets of comparative analyses prepared, each predicated on different combinations of device generation, voltage, and single vs. double treatment. The planned comparisons are outlined below.

Comparison Set 1

Device Generation 1 / 600 Volts / Single Treatment vs.

Device Generation 1 / 600 Volts / Double Treatment vs.

Device Generation 2 / 750 Volts / Double Treatment

Comparison Set 2

Device Generation 1 / 600 Volts / Single Treatment vs.

Device Generation 1 / 600 Volts / Double Treatment plus Device Generation 2 / 750 Volts / Double Treatment

Supportive individual patient data Listings will be sorted and presented by site number, patient number and visit date, if applicable. Listings will also include the number of days relative to the DMR index procedure. Specific algorithms are discussed for imputing missing or partially missing data, if deemed appropriate, under specific data topics. Imputed or derived data will be flagged in the individual patient data Listings. Imputed data, restricted to dates, will not be incorporated into any raw or primary datasets from the electronic capture system. The imputed data will be retained in the derived / analysis datasets.

Summary statistics will consist of the number and percentage of responses or counts at each level for categorical variables (e.g. race). For continuous variables, and the sample size (n), mean, median, standard deviation (SD), minimum, and maximum values will be presented.

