All mean and median values will be formatted to one more decimal place than the measured value. Standard deviation values will be formatted to two more decimal places than the measured value. Minimum and maximum values will be presented with the same number of decimal places as the measured value.

The number and percentage of responses will be presented in the form XX (XX.X%).

- All summary tables will include the analysis population sample size (i.e., number of patients).
- Relative Study Day 1 is defined as the day the patient underwent the DMR study procedure. All study days are determined relative to the day the patient underwent the DMR study procedure.
- Baseline values will be defined as those values recorded immediately prior to the DMR study procedure.
- Change from baseline for ratio data will be calculated as follows:
$$\text{Change} = \text{Post-Procedure value} / \text{baseline value}.$$
- Change from baseline for differences will be calculated as follows:
$$\text{Change} = \text{Post- Procedure value} - \text{baseline value}.$$
- Missing data may have an impact upon the interpretation of the trial data. However, given the feasibility nature of this study, coupled with the number of patients within a Comparison Set, multiple imputation will not be attempted. The primary presentation of the results will be based on the observed data. A methodology is defined in this section for addressing missing dates.
- Date variables will be formatted as DDMMYY for presentation; SAS Date9. format.
- Months will be converted to days by dividing by 30.42 and rounding up to achieve an integer value.
- SAS® Version 9.4 will be the statistical software package used for all data analyses.
- All data from this study will be presented in a listing.
- Table and listing numbering will follow ICH guidelines for post-text table and listing numbering.

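### SAP 8.6 prints expanded visit windows that overlap on four days and gives Week 48 two different windows, with no rule to choose between them

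*SAP*

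**What the plan says.** SAP Section 8.6 holds two tables. The first lists, for each visit, the code, the week, the protocol window with its first and last day, the expanded window's first and last day, and a half-width. Three of the rows at issue read:

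- "Week 8 R7 8 ±7 49 63 38 74 18"
- "Week 12 R8 12 ±7 77 91 73 95 11"
- "Week 40 R15 40 ±17 273 287 264 296 16"

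The Week 44 row gives an expanded window of 295–321 (half-width 13). The Week 48 row gives a protocol window of 306–366 (printed as 30), an expanded window of 322–366, and a half-width of 14.

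The second table lists only a target day and a half-width, defined as the number of days to each side of the target. Week 48 is target 336, half-width 14.

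The only tie rule is: "If there are multiple records within an interval, date of the latest record will be used".

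The tables are introduced for unscheduled records: "The table below provides the specification for assignment of an unscheduled visit". SAP Section 7 extends the expanded windows to the Level 3 displays, where "rows will be repeated for all visits where a measurement is recorded using the expanded time windows".

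On day numbering, SAP Section 7 states: "Relative Study Day 1 is defined as the day the patient underwent the DMR study procedure". SAP Section 9 counts primary-endpoint events up to relative study day 84, while Section 9.1 asks about events within 12 weeks of the procedure, given as 84 days.

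The ninth secondary endpoint (SAP Sections 4.2.1 and 9) counts a 24-week HbA1c responder as not having achieved it when the improvement is not maintained at 48 weeks, whatever the cause. Patients who did not respond at 24 weeks are left out of that tabulation.

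**The concern.** A visit-window table should send each study day to at most one visit. Here four days go to two visits, and the tie rule settles a different question: it chooses among several records in one interval, not between two intervals for one record. It can also make the overlap worse. A record on day 73 or 74 is the latest possible in the Week 8 window, so it would displace an on-target Week 8 record. If nothing later is recorded by day 95, it would serve as Week 12 too. Days 295–296 behave the same way for Weeks 40 and 44.

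For Week 48, two programmers working from the same section could build different datasets. One would keep records on days 351–366 and the other would assign them to no visit. In the ninth secondary endpoint a missing Week 48 value could then be read as failure to maintain. The SAP Introduction gives groups of 3, 7 and 10 patients, so one patient carries weight.

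The day origin raises a related problem for the primary safety endpoint: Sections 9 and 9.1 put its cut-off on different days if the Section 7 definition is applied literally.

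**Working it through.** **Inputs.** Target days, half-widths and printed intervals for the 14 post-procedure visits come from SAP 8.6. The day-numbering definition is in SAP 7, and the primary-endpoint cut-off in SAP 9 and 9.1.

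**Step 1: reproduce the printed expanded windows.** Window = target ± half-width.

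| Visit | Calculation | Result | Printed |
|---|---|---|---|
| Week 8 | 56 ± 18 | 38–74 | 38–74 |
| Week 12 | 84 ± 11 | 73–95 | 73–95 |
| Week 40 | 280 ± 16 | 264–296 | 264–296 |
| Week 44 | 308 ± 13 | 295–321 | 295–321 |
| Week 48 | 336 ± 14 | 322–350 | 322–366 |

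Thirteen of the 14 visits reproduce. Only Week 48 does not.

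**Step 2: check adjacent pairs.** Gap = next first day − previous last day − 1. Zero is contiguous and a negative value is an overlap.

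- Week 8 / Week 12: 73 − 74 − 1 = −2, so days 73 and 74 are shared.
- Week 40 / Week 44: 295 − 296 − 1 = −2, so days 295 and 296 are shared.
- The other 11 of 13 pairs give 0.

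The half-widths alone show the same thing. Targets 28 days apart are contiguous when their half-widths sum to 27, as with Weeks 12 and 16 (11 + 16). Weeks 8 and 12 sum to 18 + 11 = 29, and Weeks 40 and 44 to 16 + 13 = 29. Both tables therefore carry the same overlaps, which rules out a misread interval. Exact contiguity elsewhere shows that non-overlap was intended.

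**Step 3: find the nearer target for the shared days.**

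- Days 73–74 are 17–18 days from Week 8 (56) and 11–10 days from Week 12 (84).
- Days 295–296 are 15–16 days from Week 40 (280) and 13–12 days from Week 44 (308).

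All four days are nearer the later visit.

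**Step 4: size the Week 48 conflict.** The two versions differ on days 351–366, which is 366 − 350 = 16 days. Whether a visit on those days is allowed depends on the protocol window:

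- +30 gives 336–366 (31 days), of which ±14 would leave out 16.
- ±7 gives 329–343 (15 days), of which ±14 would leave out none.

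Protocol Appendix 2 prints its window row twice. One copy lines +30 up with Week 48; the other has an extra ±7 ahead of it, which would put ±7 at Week 48. The SAP's own 30 in the Week 48 row favours the +30 reading.

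**Step 5: weigh one patient in the ninth secondary endpoint.** The denominator is 24-week responders, so at most 20 overall and at most 10, 7 or 3 by group. One patient moves the proportion by at least 1/20 = 5 points overall, and by at least 1/10 = 10, 1/7 = 14.3 or 1/3 = 33.3 points within a group.

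**Step 6: check the day origin.** The targets equal 7 × week (84 for Week 12, 336 for Week 48), which counts the procedure as Day 0. With the procedure as Day 1, the same visits fall on days 85 and 337. Relative study day 84 is then 84 − 1 = 83 days after the procedure, against 84 days in SAP 9.1. An event exactly 84 days after the procedure would count under 9.1 but not under 9.

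**The case against.** Much of the case for a narrow reading stands.

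- **Week 48 loss is conditional.** A reader might infer that allowed Week 48 visits will be lost. The first table prints 322–366, which contains all of 336–366. Only a programmer who sets that interval aside and codes ±14 loses anything.
- **The share of permitted days lost is not secure.** A reader might take 16 of 31 as established. It rests on one of two conflicting copies of the schedule row, in Protocol No. 196. The SAP is written for REGENT-1-US, Doc. No. 346, so the supplied protocol cannot settle the point.
- **Reach is limited.** A reader might infer that these windows reassign every scheduled visit. Section 8.6 is written for unscheduled records, and Section 7 extends the expanded windows to the Level 3 displays. Neither says that a visit already entered as Week 48 is reclassified or discarded, so scoring such a patient as a failure is a possibility and not a stated rule.
- **Key glycemic results are largely spared by the overlaps.** SAP 9 prespecifies HbA1c, FPG and HOMA-IR at Weeks 4, 12, 24, 36 and 48. A day 73–74 record has one prespecified destination (Week 12), and a day 295–296 record has none. The Week 24 window (152–184) is contiguous with its neighbours.
- **Another overlap is harmless for analysis.** The Week 48 protocol window of 306–366 overlaps Week 44's 301–315 on 10 days. The displays use the expanded columns, so this is a table error without a shown effect.
- **The study is small and descriptive.** It has 20 patients and no formal hypothesis tests.

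These points limit the consequences. They do not remove the two overlaps, the missing rule or the two Week 48 windows, all of which lie within the SAP.

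**Conclusion.** The SAP contradicts itself on its visit windows, and this can be shown without the protocol. Two pairs of expanded windows share two days each with no rule for the shared days, and Week 48 has two windows that differ on 16 days. The effect is confined to unscheduled records and the Level 3 by-visit displays.

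A wrongly scored Week 48 patient requires three things together: ±14 is programmed, the governing protocol allows visits on days 351–366, and the window is applied to that patient's record. The SAP's own 30 and one copy of the schedule support the second condition. The documents do not establish the first or the third.

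The day-origin inconsistency is separate and worth one day. It bears on the primary safety endpoint only for an event exactly 84 days after the procedure. Nothing in the documents shows that a result would change.

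This should be corrected before the data are seen, because choosing a window or tie rule afterwards would be post hoc.

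**What to change.** Correct SAP 8.6 and the related text before programming and database lock:

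1. End the Week 8 expanded window at day 72 (38–72) and the Week 40 window at day 294 (264–294). The shared days then go to the nearer target and every adjacent pair is contiguous. Leave the other windows as they are. Re-splitting all of them at midpoints would move sound ones, including Week 24, for no gain.
2. Print Week 48 as 322–366 (−14/+30) in both tables. Week 8 becomes −18/+16 and Week 40 becomes −16/+14, so the second table needs separate minus and plus columns in place of one half-width.
3. Check the Week 48 protocol window (306–366) against the governing protocol and correct it. In the same pass, correct the Week 40 protocol window, printed as ±17 beside 273–287, which is 280 ± 7.
4. Use one day origin for the windows and the primary-endpoint cut-off. Either call the procedure Day 0, which leaves the printed targets and the 84-day cut-off as they stand, or keep Day 1 and move both up by one day. Align the Study Day 1 wording in SAP 10.1.2 with the choice.

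The cost is a table and text correction in the SAP, with no change to data collection or sample size.

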7.12.6 Premature Discontinuation

If a participant discontinues the study prematurely prior to his/her 24-week visit, to the extent possible, the participant should be scheduled for an onsite visit (V17A on SoA, Appendix 2), and the following assessments/procedures should be performed.

- Body weight, calculation of BMI, waist circumference
- Vital signs
- Concomitant medications
- Assessment of AEs that occurred since the last visit
- Hematology (CBC)
- Glycemic parameters (FPG, HbA1C, fasting insulin, HOMA-IR, MMTT)
- Comprehensive metabolic panel
- Fasting lipid panel
- Serum iron, transferrin, saturation, ferritin, serum folate, Vitamin D, Vitamin B12
- CGM data
- Diabetes and medication review by treating physician
- Lifestyle modification counseling
- Study exit

If premature discontinuation is decided during a scheduled visit, the visit will be converted to a V17A and assessment procedures should be performed accordingly.

If a participant discontinues the study prematurely after his/her 24-week visit, a remote visit (R17A) should be scheduled. The following tasks will be performed.

- Concomitant medications
- Assessment of AEs that occurred since the last visit
- CGM data, if available
- Study exit

The primary reason for premature study discontinuation must be documented on the eCRF.

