7.3. Handling of Missing Data

7.3.1. Missing and Censored Data

All tabulations and analyses will be based on the observed data without imputation, with the exception of dates.

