9. ENDPOINTS ANALYSES

There is a single primary endpoint and 18 secondary endpoints. Based on the feasibility nature of this study, there are no formal hypothesis tests.

Primary Endpoint

The primary endpoint of the study is predicated on safety; the distribution of this endpoint is binary. The primary population for analysis of this endpoint will be the ITT population.

Proportion of patients experiencing one or more device- or procedure-related serious adverse events at 12 weeks post-procedure.

All device-related or procedure-related serious adverse events from the start of the study procedure through relative study day 84 will be used in the tabulation.

The secondary endpoints are listed below:

First Secondary Endpoint

The distribution of this endpoint is binary. The primary population for analysis of this endpoint will be the FAS population.

Procedure success: defined as successful treatment of at least 6 cm of duodenum segment.

Immediately following the study procedure, a determination will be made regarding treatment of ≥ 6 cm of the duodenum. Patients who fail to have ≥ 6 cm of the duodenum treated, for any reason, will be counted as not having achieved **Procedure Success**.

Second Secondary Endpoint

The distribution of this endpoint is continuous. The primary population for analysis of this endpoint will be the FAS population.

Procedure time: defined as the time between the Endogenex catheter insertion and the catheter removal.

Procedure Time will be reported in minutes.

Third Secondary Endpoint

The distribution of this endpoint is continuous. The primary population for analysis of this endpoint will be the FAS population.

Change from baseline (post-baseline minus baseline) in HbA1c reported for each pre-specified study visit.

The pre-specified study visits where HbA1c is recorded is Week 4, 12, 24, 36, 48.

Fourth Secondary Endpoint

The distribution of this endpoint is continuous. The primary population for analysis of this endpoint will be the FAS population.

Change from baseline (post-baseline minus baseline) in Fasting plasma glucose (FPG) reported for each pre-specified study visit.

The pre-specified study visits where FPG is recorded is Week 4, 12, 24, 36, 48.

Fifth Secondary Endpoint

The distribution of this endpoint is continuous. The primary population for analysis of this endpoint will be the FAS population.

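### One four-weekly visit grid labels off-schedule HbA1c, FPG and HOMA-IR values as visits with no planned estimate, and it has no rule for the early-exit visit

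*SAP*

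**What the plan says.** - SAP 8.6 draws on records whose visit name is Unscheduled and states: "The table below provides the specification for assignment of an unscheduled visit". The one table gives windows to 14 post-procedure visits (Weeks 1, 2 and 4, then every four weeks to Week 48). It has no version by test and no row for V17A. Within a window: "If there are multiple records within an interval, date of the latest record will be used".
- SAP 7, on the Level 3 (by-visit) display: "rows will be repeated for all visits where a measurement is recorded using the expanded time windows". SAP 9.2 assigns the continuous repeated endpoints to Level 3 tables.
- SAP 9: "The pre-specified study visits where HbA1c is recorded is Week 4, 12, 24, 36, 48"; "The pre-specified study visits where FPG is recorded is Week 4, 12, 24, 36, 48". HOMA-IR has the same list, and so does post-prandial glucose from the meal test.
- SAP 4.2.1 makes Week 24 the principal time point for HbA1c, FPG and HOMA-IR, and Week 12 for the meal test. Estimates come from a repeated-measures mixed model, but the visits that enter it are not specified.
- SAP 7.3.1: "All tabulations and analyses will be based on the observed data without imputation, with the exception of dates".
- Protocol 7.12.6 collects HbA1c, FPG, fasting insulin, HOMA-IR and the meal test at V17A, for exits before the Week 24 visit. The exit visit after Week 24 (R17A) lists none of them.
- The schedule in Protocol Appendix 2 appears to place the post-procedure meal test at Weeks 12 and 48 only, against five visits in SAP 9.

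**The concern.** A glycemic test done off schedule is labelled by the nearest slot in a clinic calendar, not by the planned assessment that it could stand for. An unscheduled HbA1c on day 140 becomes Week 20, where no HbA1c estimate is planned, and cannot supply Week 24. With no imputation, the planned visit then stays empty for that patient, or the Level 3 rule prints a Week 20 HbA1c row for whoever happened to be tested.

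Off-schedule values are foreseeable. Week 12 is a remote visit (R8) in both documents, yet Protocol 7.8 says that the meal test requires attendance at the testing laboratory. Protocol 7.12.6 also converts a scheduled visit into V17A when discontinuation is decided there, so even an on-time value may carry a label that the table does not contain. With 20 patients, one value more or less at a visit is 1/20 = 5% of the data at that visit, or 1/3 of the single-treatment group (n = 3).

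**Working it through.** **1. Reproduce the printed windows.** Inputs from SAP 8.6: target day = 7 × week, and the column "Number of Days on Either Side of the Target Day to define the Expanded Time Window". Target ± width gives the printed first and last days for 13 of 14 visits, for example Week 12: 84 ± 11 = 73–95. Week 48 is the exception: 336 ± 14 = 322–350, but 322–366 is printed. The printed limits are used below.

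**2. Days inside the planned HbA1c, FPG and HOMA-IR windows.**

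| Visit | Printed window | Days |
|---|---|---|
| Week 4 | 19–37 | 19 |
| Week 12 | 73–95 | 23 |
| Week 24 | 152–184 | 33 |
| Week 36 | 241–263 | 23 |
| Week 48 | 322–366 | 45 |
| Total | | 143 |

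Days 5 to 366 number 362, so 143/362 = 39.5% are covered and 362 − 143 = 219 (60.5%) fall only in other visits. Days 73–74, which lie in both Week 8 and Week 12, are counted as covered. Counting from day 19, where Week 4 starts, 205/348 = 58.9% are uncovered. If Week 48 ended at day 350, it would be 219/346 = 63.3%.

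**3. Days sent to the farther visit.**

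| Adjacent targets | Midpoint | Boundary as printed | Days nearer the planned visit but placed in its neighbour |
|---|---|---|---|
| Week 8 (56, ±18), Week 12 (84, ±11) | 70 | Week 12 starts 73 | 71–72 |
| Week 12 (84, ±11), Week 16 (112, ±16) | 98 | Week 12 ends 95 | 96–97 |
| Week 32 (224, ±16), Week 36 (252, ±11) | 238 | Week 36 starts 241 | 239–240 |
| Week 36 (252, ±11), Week 40 (280, ±16) | 266 | Week 36 ends 263 | 264–265 |

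For example, day 96 is 96 − 84 = 12 days from Week 12 and 112 − 96 = 16 days from Week 16, but is labelled Week 16.

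**4. Meal test.** Under the five visits in SAP 9, coverage is the same 143/362. Under Weeks 12 and 48 only, it is (23 + 45)/362 = 68/362 = 18.8%.

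**5. Early exit before Week 24.** If V17A values were placed by day on this grid, the planned HbA1c windows would cover 19 + 23 + 16 (days 152–167) = 58 of the 163 days from 5 to 167 (35.6%). This is conditional, because the SAP gives no rule for V17A.

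**6. Effect of test-specific windows.** Midpoints between 28, 84, 168, 252 and 336 are days 56, 126, 210 and 294. With these, 0 of the 348 days from 19 to 366 fall outside a planned visit, against 205 on the printed grid. Day 110 moves from Week 16 to Week 12, day 140 from Week 20 to Week 24, and day 230 from Week 32 to Week 36.

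**The case against.** The strongest reply is that the table is narrower than it looks. It is written for records named Unscheduled. A late Week 12 test entered under its own visit name need not be relabelled, and Protocol 8.3 tells sites to reschedule missed visits. That stands: a reader might infer that every result is reassigned by this grid, and SAP 8.6 does not say so. The only wider reach is the Level 3 wording in SAP 7.

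A reader might also infer that off-schedule values are discarded. No section says that. The Level 3 rule gives them a row, SAP 8.5 keeps unscheduled laboratory values in a listing, and the model's visit set is unspecified. What survives is that neither reading is satisfactory: the planned estimate goes without the value, or an unplanned row appears.

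Nor do the documents place V17A values in a non-efficacy visit. V17A is a named visit with no rule at all, so the defect is an omission.

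Finally, these are secondary endpoints in a feasibility study without formal hypothesis tests, and the Week 4 to Week 36 expanded windows are already wider than the protocol's. That limits the weight of the point. It does not explain why Weeks 12 and 36 are narrower than neighbours where the test is not scheduled.

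**Conclusion.** The point holds for unscheduled records and, through the Level 3 display, for the by-visit efficacy tables. On 219 of 362 days (60.5%), an HbA1c, FPG or HOMA-IR value assigned by day is labelled as a visit with no planned estimate. On eight further-checked days around Weeks 12 and 36, the label is the farther visit, and Week 12 is the principal meal-test time point. A rule for V17A is missing.

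The percentages count calendar days. It is tempting to read them as a share of patients or values lost, or to conclude that results are biased toward patients who attend on time. The documents give no dropout rate and no distribution of off-schedule tests, so neither follows.

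Two assumptions matter. The V17A content comes from Protocol 196, while the SAP cites REGENT-1-US, Doc. No. 346; it is assumed to apply, as the visit codes match. The 18.8% meal-test coverage applies only if the test is scheduled at Weeks 12 and 48. SAP 9 lists five visits, and the two passages must be reconciled. The conflict within the SAP for HbA1c, FPG and HOMA-IR depends on neither.

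**What to change.** Before database lock:

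- For each test, assign unscheduled and V17A values to the nearest target day among the visits where that test is scheduled. For HbA1c, FPG and HOMA-IR, cut at days 56, 126, 210 and 294, with a stated tie rule and a stated earliest day for Week 4 (the printed grid starts it at day 19).
- Derive cut-points for the meal test, lipids and ALT/AST from their own reconciled schedules, with a stated maximum distance. With meal tests at Weeks 12 and 48 only, the midpoint is (84 + 336)/2 = day 210, which is 126 days from either target.
- Use the scheduled value first, otherwise the value nearest the target day. Do not use values taken after a post-Week-24 medication change for Week 24.
- For measures taken every four weeks, keep the grid but cut it at midpoints.
- For the 24-week and 48-week HbA1c responder endpoints, keep the visit-specific window and the SAP 9 rule that counts a patient as a non-achiever whatever the reason, so that early-exit values cannot create responders. Days 152–167 precede the Week 24 target but lie inside its printed window, so say explicitly that V17A values there do not count.

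The cost is SAP text and programming only. The downside is that some HbA1c, FPG and HOMA-IR values will lie up to 6 weeks from target (day 126 is 42 days from both 84 and 168). Show days from target and repeat the analyses with the protocol windows. The primary safety endpoint does not change.
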